### **6.8.3 Exploratory Aim c) To explore the feasibility and acceptability of collecting hair samples to examine changes in stress reactivity.**

Feasibility and acceptability: Feasibility metrics for the hair sampling include hair return rates. For measures of acceptability, response frequencies will summarize quantitative feedback from question 13 on the 3RP-AYA Acceptability Questionnaire (Appendix 8.15) about the acceptability of hair collection procedures. Together with qualitative feedback from the Exit Interviews (Appendix 8.29), this information will be used to inform the feasibility and acceptability of hair cortisol measurement.. Hair cortisol samples will be analyzed by [name] laboratory at the University of Massachusetts, Amherst.

Preliminary effects: We will examine group differences in HCC at T1 using independent samples T-tests. Pearson correlation or Spearman's rank correlation will examine the association of HCC with each of our psychological outcomes, controlling for potential confounders.

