## 2.2. Exploratory Aims:

a) Using a randomized, waitlist controlled design, we will examine the preliminary effects of the 3RP-AYA on stress and stress management among AYAs. Specifically, we will examine the preliminary effects of the 3RP-AYA on psychosocial measures of mindfulness, depressed mood, anxiety and stress collected at three timepoints, as detailed below: T0 (baseline), T1 (IG: posttreatment, WG: baseline2), T2 (IG: 3 month follow-up, WG: posttreatment).

Exploratory *Hypothesis 2.2a:* Compared to the waitlist-controlled group (WG), the immediate start intervention group (IG) will demonstrate greater mindfulness, lower depressed mood, anxiety and perceived stress at post-treatment. Additionally, the immediate start intervention group (IG) and waitlist control group (WG) combined will demonstrate greater mindfulness, less depressed mood, anxiety and perceived stress at treatment completion (T0-T1 for IG; T1-T2 for WG).

b) We will explore the feasibility and acceptability of collecting hair samples to examine intervention-related changes in cortisol, a stress biomarker. *Exploratory Hypothesis 2.2b2b:* The 3RP-AYA group will demonstrate lower stress reactivity (as manifested by hair cortisol) at timepoint 1 (post-treatment for IG; baseline/waitlist period for WG).

c) In efforts to inform the literature and guide future studies on engaging AYA in psychosocial treatment, we, we will examine AYA reasons for deciding not to participate in this behavioral trial. *Exploratory Hypothesis 2.2c: Participants approached about the study who choose not to participate will do so for a variety of reasons, such as time constraints.*

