**5.2.3a Hair Cortisol Measurement:** Participants will be asked to provide hair samples to measure potential changes in cortisol (“stress hormone”); this method has been used successfully in stress studies and is currently being utilized in our sister 3RP protocols [name] is leading (Partners IRB Protocol #: 2016P001622; DF/HCC #17-063, PI: [name]). Hair grows roughly 1cm/month, thus ensuring sufficient growth for collection. The RA will mail or email detailed sampling instructions (Appendix 8.16) and stamped, addressed envelopes to facilitate returns. Participants will be instructed to provide one hair sample at baseline and one sample at the end of the intervention. Specifically, they will be instructed to cut a small sample of hair (approximately 150 strands, about the diameter of a pencil eraser) from the back of their head, as close to the scalp as possible. They will be asked to tie the strands near the scalp end, place the sample in aluminum foil, and mail to MGH. The hair sampling instructions also include 6 questions about hair care, exercise, and glucocorticoid use, as these can affect hair cortisol measurements. Hair samples will not be collected from participants who have taken glucocorticoid medications (e.g. prednisone) within the past 3 months, as these medications cause cortisol measurements to be inaccurate. However, hair that is chemically treated or dyed may still be used for hair cortisol analysis. We will track the reasons why any hair samples were not collected, as this informs the feasibility and acceptability of hair cortisol collection and analysis for this population.

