## 5.6 Description of Study Process

**5.6.1 Instrument Administration:** The Baseline (Timepoint 0), Post-3RP (Timeline 1), and 3-month Follow-up (Timeline 2) Questionnaires will be self-administered by participants either on paper or electronically via REDCap survey in accordance with patient preferences. Patients may also elect to complete the questionnaires at home and mail them back to the study staff in a stamped, pre-addressed envelope, or complete them with a member of study staff over the phone, via secure videoconferencing, or in clinic. Patients may be recruited for the study and enrolled when they become available for an upcoming intervention or WCG session in the future. As outlined in Section 4.4, participants will not be registered on the study until they complete the baseline questionnaire and are randomized. The Timepoint 1 (Post-3RP data collection for the intervention group and baseline data collection for the WCG) may be completed up to approximately 12 weeks (+/- 2 weeks) after Timepoint 0, and Timepoint 2 (Follow-up data collection for the intervention group and Post-3RP data collection for the WCG) may be completed approximately 24-weeks (+/- 2 weeks) after Timepoint 0.

**5.6.2 Hair Cortisol:** Similar to other studies which have utilized hair sample collection for cortisol measurement (Partners IRB Protocol#: 2016P001622; DF/HCC #17-063), participants will be asked to cut a small amount of hair (approximately 150 strands, which is about the diameter of a pencil eraser) as close to the scalp as possible (about 3 cm), and from the back of their head. They will be asked to band or tie the strands near the scalp end, place on the sample in aluminum foil, and return in an envelope to MGH. Participants will be sent detailed sampling instructions (Appendix 8.16) and stamped, addressed envelopes to facilitate mailing. Study staff will explain the purpose of hair collection to participants to facilitate transparency of the study and invite participants the opportunity to learn more about their stress levels. A member of study staff will review the sampling procedures in detail with participants either in-person at MGH or during the brief test call, according to patient preferences and availability. Participants will be asked to provide hair samples at Timepoints 0 and 1. Participants will also be provided with the Hair Cortisol Results

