Form (Appendix 8.19), which will give participants the option to receive the results of their hair cortisol levels via a phone or secure videoconferencing conversation with the study PI, which will be scheduled after the completion of all study activities.

**5.6.3 Intervention Administration:** The 3RP-AYA will be administered virtually via Partners Telehealth videoconferencing software by the PI or by a member of the study team who has doctoral-level training in clinical psychology or medicine and is experienced in conducting the 3RP (e.g. clinical psychologists, fellows, post-docs). The 3RP-AYA consists of eight, 90-minute weekly RR-training group sessions conducted over the course of approximately 8 weeks, and there will be up to approximately 8 participants per group. The topics addressed in the eight 3RP-AYA sessions are listed in Appendix 8.18. As described in protocol section 4.2, in order to facilitate proficiency with the Telemedicine software, participants may test the software with a study staff member during a brief test call prior to the start of the intervention.

**5.6.4 Special Concerns:** Some participants may feel uncomfortable sending us a hair sample; participants will not be required to participate in the hair sample collection if they feel uncomfortable or are otherwise unable to provide a hair sample. Participants can still remain in the study if they do not wish to complete a hair cortisol sample. Additionally, some subjects may not wish to participate in the qualitative exit interview for the study; this component of the study will also be considered optional.

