### **6.8.2 Exploratory Aim b) We will examine the preliminary effects of the intervention on psychosocial measures of fatigue, mindfulness, depressed mood, anxiety, and stress.**

Preliminary outcome data may be used to inform future assessment instruments and methods. We may also conduct exploratory hypothesis testing to examine preliminary changes in our proposed intervention targets (changes in psychosocial outcomes, including mindfulness, depressed mood, anxiety, stress). A priori statistical tests of intervention-related changes will be planned for a future efficacy trial of this intervention.

First, we will examine the frequency distributions of all variables. Potential variables of interest (e.g., gender, history of RR practice) will be included as covariates if they are significantly correlated with each outcome of interest at  $p < .25$ . We will compare the baseline characteristics of completers vs. study non-completers. The primary analysis will be a completer analysis limited to those with complete data, and we will conduct a sensitivity analysis using multiple imputation for missing data.

First, we will examine between group differences in change scores in our exploratory psychosocial outcomes from enrollment (T0) to T1 (post-treatment for IG, 3-months post-enrollment/baseline #2 for WG). To further explore preliminary efficacy, we will evaluate within-group change from pre- to post-intervention (using T0 to T1 data for the IG and T1 to T2 data for the WG) for each condition separately, and then for both groups combined. Finally, within the IG only, we will explore potential maintenance of intervention benefits with a repeated measures ANOVA, including the 3 survey timepoints.

Exit interviews (Appendix 8.29) will be audio-recorded and transcribed; NVIVO software will be utilized in the thematic analysis, which will be led by members of the study staff under the mentorship of [name]. Coders will meet on a weekly basis to discuss the coding framework, categories, and coding plan. To ensure coding reliability, coding discrepancies will be resolved through discussion and comparison of raw data. Coding will continue until a high level of reliability ( $Kappa = >0.80$ ) is established.

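### Hair cortisol is compared between arms at T1 without using the T0 sample that is collected: valid, but less precise than it could be (low importance)

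*Combined protocol and SAP*

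**What the plan says.** All references are to the combined protocol and SAP.

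- **Aim.** Section 2.2b describes "collecting hair samples to examine intervention-related changes in cortisol, a stress biomarker". Its hypothesis is set at timepoint 1, when the immediate arm is post-treatment and the waitlist arm is still waiting.
- **Collection.** Section 5.6.2: "Participants will be asked to provide hair samples at Timepoints 0 and 1". The section 5.5 schedule agrees, with hair at baseline and post-3RP and none at follow-up.
- **Gaps in collection.** Section 5.2.3a: "Hair samples will not be collected from participants who have taken glucocorticoid medications (e.g. prednisone) within the past 3 months". Section 5.6.4: "participants will not be required to participate in the hair sample collection if they feel uncomfortable".
- **Between-arm hair analysis.** Section 6.8.3: "We will examine group differences in HCC at T1 using independent samples T-tests". The confounder adjustment mentioned there belongs to the following sentence, on correlations with psychological outcomes.
- **Psychosocial analysis.** Section 6.8.2: "we will examine between group differences in change scores in our exploratory psychosocial outcomes from enrollment (T0) to T1". It adds "Potential variables of interest (e.g., gender, history of RR practice) will be included as covariates", subject to a p<.25 screen, and "The primary analysis will be a completer analysis limited to those with complete data", with multiple imputation as a sensitivity analysis.
- **Delivery.** Sections 5.3 and 5.6.3 have the programme given in groups of up to about 8. Under section 5.4.3 the waitlist arm enrols and completes baseline alongside the immediate arm, and repeats the baseline before its own treatment. No analysis section mentions the treatment group.
- **Second hair sample.** Section 5.2.3a places it when the programme finishes; section 5.6.2 places it at Timepoint 1.

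**The concern.** The trial asks participants for a baseline hair sample, pays for it, and states an aim about change, yet the only between-arm hair test leaves that sample out. With about 30 completers per arm and no stratification, a baseline measure of the same quantity is the obvious means of tightening the estimate and allowing for chance imbalance. At stake is the width of the interval for one exploratory biomarker.

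The second strand is independence. At T1 one arm has been through group sessions and the other has not, while every planned T1 comparison treats participants as independent. If membership of a particular group shifts its members' outcomes together, the standard errors are too small.

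**Working it through.** The documents give no power or precision figure for any between-arm comparison, so there is none to reproduce. The only power statement (section 6.2) concerns session participation.

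**Inputs.** From the documents: 30 completers per arm (section 5.1), groups of up to about 8 (section 5.3), hair at T0 and T1 (section 5.6.2). Assumed, because the documents give none: T0-T1 correlation r, share q of T1 samples with no T0 pair, intraclass correlation (ICC), number of immediate-arm groups, and 20 per arm as a lower hair yield. Since 30/8 = 3.75, at least four groups are needed; four to six are shown.

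**Step 1: every T1 sample paired.** Variance of the T0-adjusted contrast relative to the T1-only contrast is 1 − r². The 80%-power detectable difference (two-sided 5%, noncentral t) scales by √(1 − r²).

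| r | 1 − r² | Detectable, 30 per arm | Detectable, 20 per arm |
|---|---|---|---|
| T1 only | 1 | 0.74 SD | 0.91 SD |
| 0.3 | 0.91 | 0.70 | 0.87 |
| 0.5 | 0.75 | 0.64 | 0.79 |
| 0.7 | 0.51 | 0.53 | 0.65 |

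**Step 2: some T1 samples have no T0 pair.** Relative to the T1-only test on all T1 samples:

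- complete-case ANCOVA: (1 − r²)/(1 − q)
- constrained longitudinal model (common T0 mean, known covariance, all T1 samples kept): 1/[(1 − q)/(1 − r²) + q]

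At q = 0.20 and r = 0.3 these are 0.91/0.80 = 1.14 and 1/(0.80/0.91 + 0.20) = 0.93.

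| q | r | Complete-case ANCOVA | Constrained longitudinal |
|---|---|---|---|
| 0.20 | 0.3 / 0.5 / 0.7 | 114% / 94% / 64% | 93% / 79% / 57% |
| 0.30 | 0.3 / 0.5 / 0.7 | 130% / 107% / 73% | 94% / 81% / 60% |

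Complete-case adjustment is worse than the planned test whenever r² < q. Keeping the unpaired T1 samples is better than the planned test in every cell.

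**Step 3: group effects created by the programme.** With group sizes m in the immediate arm only, the design effect there is 1 + (Σm²/Σm − 1) × ICC. With equal arms, the variance of the arm difference is multiplied by (design effect + 1)/2. The actual size of a nominal 5% test is then 2[1 − Φ(1.96/√multiplier)].

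For groups of 8, 8, 7 and 7, Σm²/Σm = 226/30 = 7.53. At ICC 0.05 the design effect is 1.327 and the multiplier 1.163, giving 6.9%.

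| Groups (30 in arm) | ICC 0.01 | ICC 0.05 | ICC 0.10 |
|---|---|---|---|
| 4 (8, 8, 7, 7) | 5.4% | 6.9% | 8.9% |
| 5 of 6 | 5.3% | 6.5% | 8.0% |
| 6 of 5 | 5.2% | 6.2% | 7.4% |

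Simulation of the t-test agrees for four and six groups.

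**Step 4: resemblance from a cohort shared by both arms.** Participants are randomised individually and the arms complete baseline together. A cohort effect common to both arms largely cancels in the arm difference. Simulating four cohorts balanced across arms, with no programme-induced effect, the t-test rejects about 4.5% of the time at cohort ICC 0.05 and 4.2% at 0.10. With both sources at 0.05, it rejects about 6.5%.

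**The case against.** The planned hair test matches hypothesis 2.2b, needs no T0 sample, and is unbiased under randomisation. Section 6.2 says the analyses are not powered to detect an effect, and section 6.8.2 defers planned tests of intervention-related change to a later efficacy trial. All of this stands. It makes T0 adjustment an efficiency gain and not the repair of an error.

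On grouping, the case against is stronger. A reader might infer that group delivery by itself makes the T1 tests too liberal. The documents do not support that: resemblance from a shared cohort leaves the t-test slightly conservative (step 4). Inflation requires effects that the programme itself creates within groups, and no document figure suggests their size. This is why the point belongs in a sensitivity analysis.

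A reader might also infer that the psychosocial analyses ignore baseline. They do not: change scores use T0. It would help to say whether the T0 score is a candidate in the p<.25 screen, but that is clarification only.

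Nor should the section 5.2.3a wording be read as a plan to take the waitlist arm's second sample at T2. Section 2.2b, the section 5.5 schedule and section 5.6.2 together point to Timepoint 1, so this is loose phrasing to tidy.

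**Conclusion.** The point holds as a low-importance improvement to an exploratory analysis. The T1-only hair comparison is sound but leaves out baseline information already being collected. Adjusting for T0 cuts the variance by 9%, 25% or 49% at r of 0.3, 0.5 or 0.7 if all samples are paired. If 20% to 30% of T1 samples lack a pair, the reduction is about 6% to 43% over the same range of r, provided the unpaired samples are kept. These are large-sample figures with known covariance and no clustering.

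The clustering strand is conditional: about 6% to 9% in place of 5%, only if programme-induced ICC is 0.05 to 0.10 with four to six immediate-arm groups. Every r, ICC, group count and missing share here is an assumption.

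It would go too far to call the planned test biased, or to promise that a fully clustered, T0-adjusted analysis will be more precise than it. A model combining retained unpaired samples with a group effect has not been evaluated for so few groups. The primary feasibility and acceptability endpoints are not touched.

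**What to change.** 1. In section 6.8.3, make the between-arm hair analysis a comparison of T1 cortisol adjusted for T0 cortisol. Keep participants with T1 but no T0 hair in this main analysis, through a constrained longitudinal model or by imputing T0. State that the completer rule in section 6.8.2 does not remove them.
2. As a sensitivity analysis beside the main T1 contrasts, report a partially nested version: group effect in the immediate arm only, small-sample degrees of freedom, and the estimated ICC.
3. Align the section 5.2.3a wording on the second hair sample with Timepoint 1 in section 5.6.2.

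The cost is SAP wording and some modelling effort, with no new data. Section 6.9 already plans multiple imputation, though only as a sensitivity analysis. The partially nested interval may be wider than that of the planned t-test: for a T0-adjusted version, up to 30% wider with four groups, ICC 0.10 and r 0.3. An ICC estimated from four to six groups will be imprecise, and the report should say so.

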### **6.9 Handing of missing data in the analysis.**

This study is intended to test the feasibility and acceptability of the stress management program. We will explore differences between study completers and non-completers on patient demographic and other relevant variables to inform the next phase of this trial. We will assess whether the mechanism of missing data is missing at random. We will perform sensitivity analysis using: 1) a completer analysis limited to those who have complete data and 2) multiple imputations for missing data. To address missing data at follow-up, participants who are no longer interested in participating in the 3RP-AYA sessions will still be given the option to complete follow-up assessments.

